## **3.5 Study Interventions / Procedures**

After enrolment, the record of each participant is examined meticulously for completeness of preoperative and postoperative data pertaining to study including:

Patient age and gender, date of the procedure and its operative notes including laterality and surgical steps.

preoperative and postoperative assessments such as uncorrected and best corrected visual acuity, refractive error quantification both objectively utilizing an autorefractometer autorefractor Nidek ARK 1 (Nidek Inc, Gamagori, Japan) and subjectively as manifest refraction, clinical slit-lamp examination notes, intraocular pressure with air puff tonometers, AC depth assessment by Pentacam Scheimpflug (Oculus Optikgeräte GmbH Inc., Wetzlar, Germany), specular microscopy study of corneal endothelial cells (endothelial cell density (ECD), coefficient of variation (CV) and hexagonality) using Topcon SP-1p Specular Microscope (Topcon Corporation, Tokyo, Japan),

Typically, there is a preoperative visit and multiple postoperative visits extending over the period of 1-2 years after the procedure.

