### 3.7 Handling of Missing Data

Section 3.5 of this protocol defines the data sets that will be collected from patients. Any missing information in this regard would be considered as incomplete data and this will meet an exclusion criterion and thereby a participant would be totally excluded from the study even if all other parameters are present.

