### 4.2 Statistical methods

After collection of data from patients records and its subjection to thorough analysis for incompleteness and exclusion criteria, these data will be stored electronically in sheet formats for later analysis. All statistical test and subsequent analyses will be performed using SPSS version 26 (IBM statistical software). Data will be classified into categorical and numerical. Categorical variables were described using frequencies and percentages and were analysed using Chi-squared test. Numerical variables, described as mean  $\pm$  standard deviation, will be subjected to tests of normality to determine the appropriate statistical tests for inter- and intra-group comparisons. Unpaired t test or Mann-Whitney test was used to compare the two groups (traditional and modified OVD) according to fulfilled statistical assumptions. These two groups were compared for statistically significant difference regarding all parameters that were collected as per section 3.5 of this protocol. These statistical comparisons were made both preoperatively to determine baseline characteristics of the study participants and postoperatively to determine any significant difference between the two groups. Within the same group whether traditional or reduced OVD, all of the aforementioned parameters were compared again pre- and postoperatively this time using either one sample paired t test or Wilcoxon signed-rank test according to fulfilled statistical assumptions. Significance was considered at P value less than 0.05.

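### The pre/post test of anterior chamber depth in section 4.2 may compare two different quantities, and section 3.7 drops a whole patient when this non-outcome measurement is missing

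*Combined protocol and SAP*

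**What the plan says.** Section 3.5 opens its list of clinical measurements with "preoperative and postoperative assessments such as uncorrected and best corrected visual acuity" and includes in the same list "AC depth assessment by Pentacam Scheimpflug". AC depth is therefore collected both before and after surgery. The section does not say to which surface the postoperative depth is measured, and it lists neither implant size nor the gap between the implant and the natural lens (vault).

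Section 4.2 applies two sets of tests to everything in that list:

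- **Between groups:** "These two groups were compared for statistically significant difference regarding all parameters that were collected as per section 3.5 of this protocol". This is done before and after surgery, with an unpaired t or Mann-Whitney test and no covariates.
- **Within each group:** "all of the aforementioned parameters were compared again pre- and postoperatively this time using either one sample paired t test or Wilcoxon signed-rank test".

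Nothing exempts AC depth from either set. Section 3.6 names unaided acuity as the primary outcome, and IOP, the specular microscopy parameters and adverse events as secondary outcomes. AC depth is not among them. Section 3.7, referring to the section 3.5 data, says "Any missing information in this regard would be considered as incomplete data and this will meet an exclusion criterion", and it removes the participant even when every other item is available.

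**The concern.** A paired test is meaningful only if the same quantity is measured at both times. The implant is a phakic lens (sections 1 and 3.3), and the complications review cited in section 7 describes this lens type as a posterior-chamber one. The natural lens stays in the eye behind it. Before surgery, depth can end only at the natural lens. Afterwards there are two candidate surfaces. If the reading stops at the implant, the paired difference contains implant thickness plus vault and would appear in any implanted eye. If the surface varies between eyes or visits, the mean mixes two quantities.

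The study asks whether leaving out dispersive OVD is safe. A significant shallowing of the chamber in the reduced-OVD group could be taken as a safety signal although it says nothing about OVD. There is also a cost to the named outcomes: a patient without a postoperative AC depth is lost from the acuity, IOP, endothelial and adverse-event analyses.

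**Working it through.** The documents state no sample size, SD, expected shift or power, so there is no figure of theirs to reproduce. The 0.05 level is from section 4.2 and is taken as two-sided. Every other input is an assumption, chosen to show a range. The unit is eyes per group.

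**Step 1. Within-group paired test, no OVD effect.** The noncentrality is shift / (SD of change / √n), referred to the noncentral t distribution with n − 1 degrees of freedom.

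| Assumed shift (mm) | SD of change (mm) | n | Noncentrality | P(significant) |
|---|---|---|---|---|
| 0.1 | 0.20 | 30 | 0.1/(0.20/√30) = 2.74 | 0.75 |
| 0.1 | 0.20 | 50 | 3.54 | 0.93 |
| 0.1 | 0.20 | 100 | 5.00 | >0.99 |
| 0.3 | 0.25 | 10 | 0.3/(0.25/√10) = 3.79 | 0.92 |
| 0.3 | 0.25 | 20 | 5.37 | >0.99 |
| 0.3 | 0.35 | 10 | 2.71 | 0.68 |
| 0.3 | 0.35 | 20 | 3.83 | 0.95 |

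Simulation (4000 runs per setting) gave 75%, 93% and over 99% for the first three rows.

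**Step 2. Between-group postoperative test, same shift in both groups.** With baseline SD 0.25 mm and SD of change 0.20 mm, the postoperative SD is √(0.25² + 0.20²) = √0.1025 = 0.32 mm. For common shifts of 0 to 0.6 mm and 30 to 100 eyes per group, the simulated rejection rate was 4.3% to 5.7%, which is the nominal level. Implant presence therefore cancels between groups.

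**Step 3. Between-group test, implant position differing between groups.** Using the normal approximation, power is Φ(difference / (0.32 × √(2/n)) − 1.96).

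| Difference (mm) | n = 30 | n = 50 | n = 100 |
|---|---|---|---|
| 0.1 | Φ(1.21 − 1.96) = 0.23 | Φ(1.56 − 1.96) = 0.35 | Φ(2.21 − 1.96) = 0.60 |
| 0.2 | 0.68 | 0.88 | 0.99 |

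With an SD of 0.30 mm instead, a two-sample t test gives 0.38 (n = 50) and 0.65 (n = 100) for 0.10 mm, and 0.70 and 0.94 for 0.15 mm.

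**Step 4. Source of a position difference.** Section 3.3 says that group membership followed the preferences of surgeon and patient, so implant size or baseline depth may be unbalanced. Section 1 says that viscoelastics help to place the implant, so technique itself could affect position. The section 4.2 test is unadjusted and section 3.5 lists neither size nor vault. A significant result would not distinguish these explanations.

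**Step 5. Exclusion rule.** This step needs no assumption about the device. AC depth is a section 3.5 item, section 3.7 excludes for any missing section 3.5 item, and section 3.6 does not name AC depth as an outcome.

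**The case against.** The strongest reply is that the plan does not use the paired tests to judge the technique. Section 4.2 gives the group question to the between-group comparisons, and a change seen in both groups would read as a result of surgery. Refraction and unaided acuity also change because of the implant, and nobody objects to testing those. The first part stands: a reader might infer that the plan presents within-group AC depth changes as OVD effects, and it does not. The analogy with acuity is weaker, because acuity is the same quantity before and after surgery, while AC depth may not be.

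Two other strong readings also fail. One is that the implant's presence would create a spurious difference between groups; Step 2 shows that it would not. The other is that postoperative AC depth could never carry an effect of technique; given the role section 1 assigns to viscoelastics in placing the implant, it could.

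It is also fair to say that no document states which surface the device reads after surgery, that every magnitude is assumed, and that confounding by preference and whole-patient exclusion are general features of this plan. All of that limits the size of the point. It does not remove the undefined paired comparison, or the loss of outcome data over a variable that is not an outcome.

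**Conclusion.** The point holds and is minor. As written, section 4.2 runs a paired test on a variable whose postoperative meaning is not fixed. If the reading moves to the implant, that test will often be significant whichever OVD was used: about 75% of studies at 30 eyes per group for an assumed 0.1 mm shift, and near certainty at that size for 0.3 mm (SD of change 0.2 mm in both cases). If depth is always read to the natural lens, this particular problem does not arise. A postoperative group difference cannot be attributed, because size or position imbalance and a real effect of technique are both possible.

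A reader might infer that the study's main conclusions are compromised. The documents do not support that: neither the primary nor any listed secondary outcome rests on AC depth. The exclusion consequence follows from the text alone, but its size is unknown because no rate of missing AC depth is given.

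**What to change.** - **Section 4.2:** use preoperative AC depth as a baseline variable and drop the within-group pre/post test of AC depth. If postoperative depth is reported, summarise it descriptively by group, to one stated surface where the records allow, and say that it is not interpreted as an effect of OVD technique. Any group contrast then stays visible to the reader without being attributed.
- **Section 3.7:** state that a missing postoperative AC depth does not exclude the patient from the acuity, IOP, endothelial and adverse-event analyses.

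The cost is a few sentences. Dropping the paired test and exempting the missing value need no new data. Reporting to a single surface may need scans to be re-read, and the documents do not show whether that is possible, hence the qualifier. What is lost is a paired test of a variable that is not a named outcome.

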## 5 Ethical Considerations

The study merely investigates the records of patients that had already undergone refractive surgeries. It followed the principles of the "Declaration of Helsinki" and local laws and regulations.

The study was approved by the institutional review committee at the respective hospital and a similar committee at the college of medicine of university of Basrah according to the local guidelines and protocols. Written informed consent was obtained from each patient before the surgery.

Patients data are to be stored safely electronically using dedicated computers for the task. Patients privacy and confidentiality was taken into account.

## 6 Study Impact and Significance

Traditionally dispersive OVDs has been used extensively during loading and implantation steps of ICL surgery. Reducing both the amount and the types of viscoelastics used (cohesive only) might potentially reduce cost and time of the procedure and might provide a substitute for safety studies regarding omitting or further reduction of cohesive OVDs and utilizing BSS only which carries lower risk of raised IOP and lower cost of the procedure.

